5.6 Phase 2: Adaptation to Ventilated Study Cigarette

During Phase 2 (baseline 92 to randomization visit 00), eligible subjects will be provided study ventilated cigarettes. Subjects will be instructed to continue to report on daily intake of tobacco and nicotine products, alcohol and marijuana in the ITR. Data will be collected during telehealth visits and biological samples for biomarker analysis collected at the brief clinic or curbside visit.

Procedures for Visit Telehealth Visit (Visit 91)

A. Physiological Measures:

- 1) CO level will be measured while conducting the telehealth visit.
- 2) Vitals signs (blood pressure, heart rate) will be obtained while conducting the telehealth visit.

B. Surveys – link sent to participant to complete REDCap based survey:

Subjective Outcome Measures:

- 1) Minnesota Nicotine Withdrawal Scale(MNWS)
- 2) Questionnaire of Smoking Urges-brief scale - Study Cigarette (QSU)
- 3) Modified Cigarette Evaluation Scale – Study Cigarettes
- 4) Respiratory Symptoms and Global Health Questionnaire
- 5) Duke Sensory Questionnaire – Study Cigarettes
- 6) BDI-II and or GAD7 will be administered for clinician to review if monitored for depression or anxiety.

C. Interviews - Research Assistant interviews participant and enters directly into REDCap:

- 1) COVID-19 Assessment
- 2) Health Changes and Menstrual Cycle Questionnaire
- 3) Adverse Events
- 4) Concomitant Medications
- 5) Daily IVR Call Review (follow-up on missing and unusual reports)
- 6) Timeline Follow Back Questionnaire
- 7) Intention to Quit
- 8) Drug accountability: Complete Dispensing Logs
- 9) Compliance Review
- 10) End of Visit Evaluation.

Supplies, sample collection containers and handouts will be provided to the participant at the Baseline 91 brief clinic or curbside visit for collection of cigarette butts, urine, saliva and blood spots for the Week 0 baseline sample collection. Participants will be asked to collect cigarette butts 24 hours prior to Visit 00.

Procedures for Visit 2 Telehealth Visit (Visit 00)

At the second Baseline visit (00), subjects will be informed that they have been randomized to either ventilated or unventilated study cigarettes. Subjects will complete several measures and provide biological samples for biomarker analysis as described below.

A. Physiological Measures and Biomarker Samples:

- 1) Vitals signs (blood pressure, heart rate) will be obtained while conducting the telehealth visit.

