- 2) Carbon monoxide level will be obtained while conducting the telehealth visit.
- 3) Biological sample collection for analysis of nicotine and carcinogen metabolites will be collected prior to (first void urine sample) or at the telehealth visit (saliva and possibly blood spots) and then dropped off at the brief clinic or curbside visit. Oral cells will be collected during the telehealth, in-person curbside or clinic visit. Subjects will be instructed to brush teeth prior to the collection.
- 4) Review Cigarette Butt Collection: The 24-hour collection of cigarette butts prior to this visit will be reviewed and dropped off at brief clinic or curbside visit. These spent filters will be analyzed for cigarette butt staining to inform intensity of smoking behavior.

B. Surveys – link sent to participant to complete REDCap based survey:

Biomarker Modifier Questionnaires:

- 1) Environmental Tobacco Smoke Questionnaire

Subjective Outcome Measures:

- 1) Minnesota Nicotine Withdrawal Scale(MWSC)
- 2) Questionnaire of Smoking Urges-Brief Scale – Study Cigarette (QSU)
- 3) Respiratory Symptoms and Global Health Questionnaire
- 4) Modified Cigarette Evaluation Scale – Study Cigarette
- 5) Perceived Health Risk
- 6) Cigarette Purchase Task – Study Cigarette
- 7) Nicotine Dependence Questionnaire
- 8) Duke Sensory Questionnaire – Study Cigarette
- 9) BDI-II and or GAD7 will be administered for clinician to review if monitored for depression or anxiety.

C. Interviews - Research Assistant interviews participant and enters directly into REDCap:

- 1) COVID-19 Assessment
- 2) Health Changes and Menstrual Cycle Questionnaire
- 3) Adverse Events
- 4) Concomitant Medications
- 5) Daily ITR Review (follow-up on missing and unusual reports)
- 6) Timeline Follow-back Questionnaire (since last visit)

- 7) Randomization to either ventilated or unventilated cigarettes - Read appropriate script
- 8) Intention to Quit
- 9) Product Accountability Log
- 10) Compliance Review
- 11) End of Visit Evaluation

Dispensing Study Product:

At the brief clinic or curbside visit, the participant will be provided their randomized study cigarettes (ventilated or unventilated). The subject will continue to be allocated 150% of their baseline cigarettes per day and receive a \$2 credit per pack for each unused pack of cigarettes that are returned in order to disincentivize wasteful use of cigarettes (sharing with friends, hoarding cigarettes; max credit up to \$30).

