The above methods will be supplemented with multiple linear regression analysis to include the baseline (visit 00) value for NNAL or CPD and the stratification variable (site), plus any other subject specific characteristics which might not be balanced between the study groups (p-value<0.2).

Finally, NNAL and CPD will be analyzed for all visits, starting at visit 00, using a linear mixed effects model (SAS PROC MIXED). The fixed effects are ventilation group indicator, plus other potential predictors. To model the variation within subjects, several candidate variance-covariance structures will be compared using both graphical and information criteria. Variance parameters will be estimated using restricted maximum likelihood method with the Satterthwaite approximation. This analysis will provide useful information about the change in toxicant exposure and the change in the number of cigarettes smoked per day over time.

Both linear regression models and repeated measures analysis can be modified for the equivalence and non-inferiority testing situations.³⁴

Secondary Endpoint Analysis

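### Does the supplementary mixed model need respecifying because it takes visit 00 as a response and names only the group term?

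*Combined protocol and SAP*

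**What the plan says.** Section 10.2 analyses each primary endpoint (NNAL and cigarettes per day, CPD) in three layers.

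- **Primary Analysis:** a one-sided two-sample t-test for non-inferiority on the change from visit 00 to Week 6, with margins of 15% for NNAL (log scale) and 2.0 cigarettes for CPD.
- **Secondary Analysis, first part:** a linear regression that includes the visit 00 value, site and any characteristics found to be unbalanced.
- **Secondary Analysis, last part:** "NNAL and CPD will be analyzed for all visits, starting at visit 00, using a linear mixed effects model". On its terms: "The fixed effects are ventilation group indicator, plus other potential predictors". On covariance: "several candidate variance-covariance structures will be compared using both graphical and information criteria". Its purpose is to give "useful information about the change in toxicant exposure and the change in the number of cigarettes smoked per day over time".

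The section closes with a general remark: "Both linear regression models and repeated measures analysis can be modified for the equivalence and non-inferiority testing situations". It names no contrast and no margin for the mixed model.

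On timing, section 5.6 says that in Phase 2 "eligible subjects will be provided study ventilated cigarettes". Randomised cigarettes are handed over only at the clinic or curbside visit that follows the visit 00 telehealth session (sections 5.6 and 5.8).

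**The concern.** At visit 00 both arms have smoked the same ventilated study cigarette for two weeks, so randomisation makes the expected arm difference zero. A model that takes visit 00 as an outcome and has one group coefficient forces a single arm difference on all visits, including the one where none can exist. Adding a visit main effect does not cure this, because the group effect is still common to all visits.

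The coefficient would then be neither the Week 6 effect nor the difference in change. The weight on visit 00 also depends on the covariance structure, which is chosen after the data are seen, so the quantity estimated would not be fixed in advance. In a non-inferiority trial, an estimate pulled toward zero leans toward the conclusion the investigators expect. An unnamed contrast also leaves room to choose what to report.

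**Working it through.** The plan states no figure for this model, so there is none to reproduce. The check asks what the coefficient would estimate under the unfavourable reading, and whether the other analyses share the problem.

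**Inputs from the documents.** NNAL responses from visit 00 onward: visits 00, 3 and 6 (section 6.2), so k = 3. Margins: ratio 1.15, or ln(1.15) = 0.1398, and 2.0 CPD (section 10.2).

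**Assumptions.** Seven CPD values (visit 00 and Weeks 1 to 6), since the plan does not say how CPD is summarised for this model; complete data; an effect δ constant after randomisation; within-subject correlation ρ of 0.5, 0.7 or 0.9; and the variance patterns below.

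**Formula.** With balanced data, group-only and group-plus-visit fits give the same group coefficient: Σ wⱼdⱼ, where dⱼ is the arm difference at visit j and w = V⁻¹1 / (1′V⁻¹1). With d = 0 at visit 00 and δ afterwards, the coefficient is (1 − w₀)δ.

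**Equal variances, compound symmetry.** w₀ = 1/k.
- NNAL: w₀ = 1/3, and 1.15^(2/3) = 1.098.
- CPD: w₀ = 1/7, and 2.0 × 6/7 = 1.71.

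**Equal variances, AR(1).** w₀ = 1/(k − (k − 2)ρ).

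| ρ | w₀, NNAL | 1.15 reads as | w₀, CPD | 2.0 reads as |
|---|---|---|---|---|
| 0.5 | 0.400 | 1.087 | 0.222 | 1.56 |
| 0.7 | 0.435 | 1.082 | 0.286 | 1.43 |
| 0.9 | 0.476 | 1.076 | 0.400 | 1.20 |

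**Unequal variance at visit 00.** Let later visits have SD 1 and visit 00 have SD s, with exchangeable correlation. The mean of the k − 1 later visits has variance v = (1 + (k − 2)ρ)/(k − 1), and its covariance with visit 00 is c = ρs. Then w₀ = (v − c)/(s² + v − 2c).

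| Endpoint | ρ | s | w₀ | Estimate |
|---|---|---|---|---|
| NNAL | 0.7 | 1.2 | 0.010/0.610 = 0.02 | 1.147 |
| NNAL | 0.7 | 1.5 | −0.20/1.00 = −0.20 | 1.183 |
| NNAL | 0.9 | 1.1 | −0.04/0.18 = −0.22 | 1.186 |
| NNAL | 0.9 | 0.8 | 0.23/0.15 = 1.53 | 0.928 |
| CPD | 0.7 | 1.1 | −0.02/0.42 = −0.05 | 2.10 |

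Dilution is therefore a feature of equal-variance structures, not of the model in general. The general statement is that the coefficient's target depends on the covariance.

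**With a group-by-visit term.** The Week 6 minus visit 00 contrast has fixed weights of +1 and −1, so its target is δ − 0 = δ (1.15 or 2.0) whichever covariance is selected.

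**The other two layers.** The t-test on change targets δ − 0 = δ. The Week 6 regression has visit 00 on the right-hand side, and randomisation makes its expected arm difference zero, so its group coefficient also targets δ. Neither is diluted.

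**The case for a change.** The strongest case for a change is that the omission is real. The text names no visit term, no group-by-visit term, no treatment of visit 00 and no contrast. Reading visit into the open-ended predictors is not enough, since a visit main effect leaves the group coefficient where it was. The section also says repeated-measures models can be adapted to non-inferiority without saying how, and a few words of specification would cost nothing.

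The under-specification stands, but not the step to a likely wrong result. The plan does not prescribe a group-only or group-plus-visit fit. The stated purpose is change over time, which neither can show, so both are poor readings of the text. The direction of error is not settled either: the claim that the coefficient would be pulled toward no difference needs equal variances, which the plan does not assume. Error rates and power from testing this coefficient against a margin would describe a test that the plan does not contain, using SDs that it does not give, so they carry no weight here.

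Nor is Week 6 the only defensible contrast. The first two layers already estimate the Week 6 effect, and a longitudinal supplement could reasonably report a trajectory or a post-randomisation average.

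**Conclusion.** No change to the plan is called for. The mixed model is thinly described, but an analyst working toward its stated purpose would include visit and group-by-visit terms, and the wording permits them.

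Under the unfavourable reading the distortion could be material: 1.15 read as 1.076 to 1.098, and 2.0 cigarettes as 1.20 to 1.71, under equal-variance compound symmetry or AR(1), or errors in either direction when visit 00 has a different variance. These sizes rest on assumed correlations and variance ratios, a constant effect after randomisation, complete data and, for CPD, seven weekly values.

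Even then no trial conclusion would move. The non-inferiority decision belongs to the t-test on change, the baseline-adjusted regression supports it, and both target the full Week 6 effect. The mixed model comes third, is descriptive, and has no margin or decision attached.

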1.2 Secondary Objectives

The secondary objectives are to examine the effects of cigarette filter ventilation on subjective measures such as cigarette dependence and responses to study cigarettes. As an exploratory analysis, the concordance for toxicant levels analyzed across multiple biosamples (urine, saliva, blood spots and hair) and subject acceptability of collecting these samples at home will be determined.

We hypothesize that unventilated filter cigarettes will be associated with no higher number of cigarettes smoked, biomarkers of exposure or cigarette dependence and satisfaction compared to ventilated filter cigarettes; but smokers assigned to the ventilated filter cigarettes will smoke cigarettes more intensely and perceive them as less harmful than smokers assigned to the unventilated cigarettes. We also hypothesize the level of toxicant exposure will be concordant across various methods of collecting biological samples.

2 Background

The Changing Cigarette. Over 34 million people in the United States,¹ and about 1.2 billion globally,² smoke cigarettes. With about 500,000 deaths per year in the US^{1,3} and 6 million per year worldwide,² it is critical to have strong tobacco control policies in place to minimize the casualties from tobacco use.

The Family Smoking Prevention and Tobacco Control Act (FSPTCA), signed into legislation in 2009, provides the FDA with the authority to regulate tobacco products. One of the provisions in this legislative act empowers the FDA to assert product standards that would reduce harmful constituents in tobacco products, including alterations in the design of the product. A product standard that requires consideration is the use of ventilation in cigarette filters. Filter ventilation came onto the marketplace in the 1960s in response to consumer concerns about the negative health impact of cigarettes after a series of reports, including the 1964 U.S. Surgeon General's Report⁴ (SGR), linked smoking to lung cancer and other diseases. Filter ventilation was a way for the tobacco industry to reduce machine-determined tar and nicotine yields in cigarettes, providing consumers with the perception that these cigarettes were "safer" to smoke. This perception, however, was false because

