5.1 Investigational Tobacco Products

Tobacco Products:

Study Cigarettes: The study cigarettes will be a conventional manufactured cigarettes (e.g., Pyramid 100 mm). The investigational cigarettes are either: 1) ventilated (e.g., 28% +/- 4% filter ventilation); or 2) unventilated (e.g., ~0-5% filter ventilation). Product characteristics including blend of tobacco, additives, nicotine and tar content levels will be identical across these two cigarettes but will differ in the degree of ventilation (number of filter vents), e.g., no ventilation or ventilation (the extent of ventilation found in former “light” to “ultra-light” cigarettes). The dose of nicotine will be similar to usual brand cigarettes. The tobacco will be tested periodically to verify constituent levels are stable.

At each visit, the subject will receive 150% of their baseline cigarettes per day. Providing additional cigarettes per day will allow for potential compensatory smoking or a potential delay in attending the brief clinic or curbside appointments. Menthol and non-menthol cigarettes will be provided, as preferred.

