10.1 Trial Endpoints

Primary Endpoint:

- The change in total NNAL from visit 00 to week 6 visit.
- The mean CPD based on 7-day IVR data between week 00 and Week 6 visit

Secondary Endpoint:

- Change in TNE, CEMA, and PheT from visit 00 to week 6 visit
- Change in intensity of smoking measured by filter analysis collected at 00, Week 3 and Week 6.
- Change in parameters of inhalation depth measured at 00 and Week 6.
- Change in subjective measures (dependence as measured by the FTND, mCES, and Perceived Health Risk) from visit 00 to Week 6 visit.

Exploratory Endpoints:

- Change in biomarkers of other volatile organic compounds (e.g.,3-HPMA, HMPMA) from visit 00 to Week 6 visit.
- Determine concordance in biomarkers of exposure across different sample collection methods.

Secondary Endpoint

Safety Endpoints:

- Adverse Events (AEs)

- Serious adverse events (SAEs)

Randomization

Subjects will be randomly assigned using a stratified (by site), block randomization scheme into the following groups: (1) ventilated filter cigarettes; or (2) unventilated filter cigarettes.

Sample size and power considerations

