The secondary analyses include the other biomarkers (as listed above). The analysis for these potential toxicants will be the same as that outlined above for NNAL with measurements at end of Phase 2 (visit 00) and at the 6 week visit. A non-inferiority margin has not been established for many of these biochemical measures. Instead, group differences or ratios (if in the log scale) will be estimated with their 95% CI and examined as to whether or not they contain 0 for differences or 1 for ratios. Inhalation measures and smoking intensity (solanesol levels in the filter butts) will be analyzed with similar methods as the change in biomarker and CPD with regression models incorporating-covariates for baseline variables that may be different between groups ($p\text{-value}<0.2$). The FTND as a measure of dependency is a composite score that ranges from 0 to 10. With the expectation of non-inferiority for the unventilated group, a linear regression model for FTND at 6 weeks will include the FTND at baseline (visit 00) and the ventilation group indicator, plus any other important subject characteristic. The 95% CI for the estimated coefficient for the group indicator will be calculated to verify that it contains the value zero, indicating no difference in dependency between ventilation groups. The mCES and PHR questionnaires produce a series of subscales. To identify differences between ventilated and unventilated groups, non-parametric methods will be utilized, first with the Wilcoxon signed rank test to check for changes from end of Phase 2 to 6 weeks within each ventilation group and then with the Wilcoxon rank sum test for differences between groups.

Exploratory Analysis

The exploratory analysis for the other volatile organic biomarkers (listed in section 6.2) will be the same as that outlined above for NNAL and the other secondary biomarkers.

Correlation procedures (Pearson and Spearman) will measure the degree of association for the same biomarkers assayed from two or more biosamples.

Safety Endpoints

AEs and SAEs will be recorded as described in the Adverse Event SOP. AEs and SAEs will be tabulated separately for the two groups. We expect study product-related AEs and SAEs to be rare in this trial and, therefore, no formal statistical comparison of the rate of AEs and SAEs across treatment groups is planned for this trial.

Missing Data

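### Change in spent-filter solanesol is read as smoking intensity although only one arm changes product, so an equal or higher deposit in the unventilated arm cannot be read as puffing intensity

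*Combined protocol and SAP*

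**What the plan says.** Smoking intensity is named in the primary aim (Study Synopsis; Section 1.1), and Section 1.2 gives it a direction: "smokers assigned to the ventilated filter cigarettes will smoke cigarettes more intensely". Section 10.1 makes it a secondary endpoint: "Change in intensity of smoking measured by filter analysis collected at 00, Week 3 and Week 6". Section 10.2 (Secondary Endpoint Analysis) identifies intensity with the solanesol level in the butts and sends it through the same kind of analysis as the biomarkers and cigarettes per day: "Inhalation measures and smoking intensity (solanesol levels in the filter butts) will be analyzed with similar methods as the change in biomarker and CPD". The only adjustment named there is for "covariates for baseline variables that may be different between groups", selected at p<0.2.

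Three other parts of the protocol bear on how that comparison reads:

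- Section 2 (Background): "Filter ventilation was a way for the tobacco industry to reduce machine-determined tar and nicotine yields in cigarettes". Machine yields are yields under fixed puffing.
- Section 5.1: the control cigarette is "ventilated (e.g., 28% +/- 4% filter ventilation", and the other has about 0-5%. Blend, additives and tar and nicotine content are otherwise the same.
- Sections 5 and 5.6: everyone smokes the ventilated study cigarette for the two weeks before visit 00, and randomisation follows.

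Section 6.2 (Spent Filter Analysis) has the filters analysed for constituent yield and vent blocking. It describes no step from those results to puffing.

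**The concern.** The visit 00 butts in both arms come from the ventilated cigarette. At Weeks 3 and 6 the ventilated arm's butts come from the same product, and the unventilated arm's come from a different one. By the protocol's own account, ventilation lowers the smoke delivered at fixed puffing. The filter deposit therefore tracks smoke drawn per cigarette, and not puffing alone. In the ventilated arm the change score reflects behaviour. In the unventilated arm it reflects behaviour plus the product switch.

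The product component pushes the unventilated deposit up, which is the opposite direction to the hypothesis. Compensatory puffing in the ventilated arm could be masked, or could appear reversed. The report might then say that removing vents left intensity unchanged, or raised it, when the data cannot show that. The same argument applies to any filter measure that scales with smoke drawn, so it does not depend on solanesol being the analyte.

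**Working it through.** **Plan's own figure.** There is none to reproduce. The documents give no sample size, margin, calibration or variance for the filter endpoint.

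**Inputs.** Ventilation v = 28% ± 4% (24-32%) and u = about 0-5% (Section 5.1, both given as examples); the same product in both arms at visit 00 (Sections 5, 5.6); 73 evaluable per group (Section 10.1, sized for NNAL).

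**Assumption (not in the documents).** The deposit is proportional to the undiluted smoke drawn through the rod, i.e. to puffing × (1 − ventilation), with vents open.

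**Step 1: what the change score contains.** On the log scale:
- ventilated arm: change = change in puffing
- unventilated arm: change = change in puffing + log[(1 − u)/(1 − v)]

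The extra term arises after randomisation and coincides exactly with the group indicator. The visit 00 value carries the factor (1 − v) in both arms, so conditioning on it, or on imbalanced baseline covariates, leaves the term in the group effect.

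**Step 2: its size.** Deposit ratio, unventilated/ventilated, at identical puffing = (1 − u)/(1 − v):

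| | u = 0% | u = 2.5% | u = 5% |
|---|---|---|---|
| v = 24% | 1.32 | 1.28 | 1.25 |
| v = 28% | 1.39 | 1.35 | 1.32 |
| v = 32% | 1.47 | 1.43 | 1.40 |

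The extremes are 0.95/0.76 = 1.25 and 1.00/0.68 = 1.47.

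**Step 3: how much compensation it hides (28% vs 0%).** If ventilated-arm smokers puff k times as intensely, the observed ratio is 1.389/k.
- k = 1.2: 1.16, still the wrong direction
- k = 1.389: 1.00, which would be read as equal intensity
- k = 1.5: 0.93, the correct direction

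**Step 4: chance that the product term alone is significant.** Power = Φ(log r / (s√(2/73)) − 1.96), two-sided 0.05, with s an assumed SD of the log change. The value 0.34 is what the NNAL sample size implies: log(1.15)/[(1.645 + 0.842)√(2/73)] = 0.340. It is borrowed only as one scenario.

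| s | r = 1.25 | r = 1.39 |
|---|---|---|
| 0.34 | 0.98 | >0.99 |
| 0.5 | 0.77 | 0.98 |
| 0.7 | 0.49 | 0.81 |
| 1.0 | 0.27 | 0.51 |

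**Step 5: vent blocking.** Suppose, for illustration, that blocking in use halves effective ventilation from 28% to 14%. The ratio at identical puffing against 0% falls to 1/0.86 = 1.16; with complete blocking it is 1.00. Scaling the ventilated deposit by the nominal 1/0.72 in the half-blocked case would show the ventilated arm 0.86/0.72 = 1.19 times as intense when puffing is identical.

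**The case against.** A reader might infer that the intensity hypothesis cannot be tested at all. The documents do not support that. The bias is one-directional and runs against the hypothesis, so a higher deposit in the ventilated arm would support it, and conservatively. Sections 5.2 and 10.1 also provide inductance plethysmography at visit 00 and Week 6 as a separate secondary endpoint that does not depend on filter deposits. It is a partial answer only: it covers a subset of unstated size and measures inhalation, not puff volume.

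A reader might also infer that the plan commits to comparing unconverted deposits. It does not say so; it is silent on conversion, and Section 6.2 plans yield and vent-blocking work. What stands is that no conversion is specified, and that an estimate of constituent yield would still measure smoke delivered, not puffing.

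Nor would the trial's whole conclusion on smoking behaviour be wrong. The filter endpoint is secondary with no margin or decision rule, and cigarettes per day is itself a co-primary behavioural outcome. An unconverted deposit is also informative for the goal in Section 2 of checking that a ventilation ban does not raise exposure.

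Finally, the size is model-based. The documents contain no machine-yield, filter-efficiency or solanesol data, and only one-cm mouth-end portions are extracted. All of this limits the size of the bias and the reach of the point. It does not remove the product switch from one arm's change score.

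**Conclusion.** The point holds for the interpretation of one secondary endpoint, and the plan should be changed. Followed as written, Section 10.2 labels as smoking intensity a between-arm contrast that contains a product effect in one arm only. A higher ventilated-arm deposit remains usable evidence for the hypothesis. The other two outcomes, equal deposits or a higher unventilated deposit, are not interpretable as puffing.

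The direction rests on the protocol's own statement about machine yields. The ratio of 1.25 to 1.47 rests on proportional dilution, open vents and the example ventilation values. That range reflects product tolerance only, so the true uncertainty is wider, and blocking would move the ratio towards 1. Whether the product term alone would reach significance depends on an SD the documents do not give: it is likely at a log-scale SD of 0.5 or below, and about even or less at 1.0 for the ratios tabulated. NNAL and cigarettes per day are not affected.

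**What to change.** 1. In Sections 10.1 and 10.2, report the unconverted filter deposit as smoke yield per cigarette (mouth-level exposure).
2. State in Section 10.2 that an equal or higher deposit in the unventilated arm is not evidence of equal or greater smoking intensity.
3. Base any intensity conclusion on a value converted separately for each study cigarette, for example from a bench calibration of deposit against known puff volume. State how the vent-blocking data already planned in Section 6.2 enter the conversion, and apply it before computing change from visit 00.
4. If only 1/(1 − v) scaling is available, do not use it at the nominal ventilation as the main result, because of the reverse bias shown in Step 5. Present it as a sensitivity analysis over effective ventilation from fully open to blocked (a factor of 1/0.72 = 1.39 down to 1.00 for a 28% cigarette), next to the unconverted yield and the subset inhalation measures.

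Items 1, 2 and 4 cost wording and a short analysis. Item 3 adds laboratory work on two products if bench calibration is chosen. None needs a new participant procedure. The downside is that the converted value is approximate and depends on assumptions about blocking and filter retention, so the unconverted yield should always be shown with it.
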